## Overall synopsis of the clinical investigation

Study title: Regular home use of dual-light photodynamic therapy as an adjunct to non-surgical periodontal treatment in smokers
Type: Investigator initiated study
Study Center: Department of Preventive Dentistry, Periodontology and Implant Biology, (AUPH) · Aristotle University of Thessaloniki
Name of the Investigational Medical Device (IMD): 1) Lumoral treatment device 2) Lumorinse mouth rinse
Manufacturer of the Investigational Device: Koite Health Oy, [name]
Study code: Thss1
Investigators and the study center: Principal Investigator: [name]; Coordinating Investigator: [name]; Investigators: [name], [name], [name], [name]
Study initiation and ending date: 01.09.2022 to 01.09.24
Objectives: To investigate the impact of regular home use of Lumoral device as an adjunct treatment compared to non-surgical periodontitis treatment alone on biofilm removal and host response in Stage III and Grade C smoking periodontitis patients at 3 months.
Methodology: Randomized study; randomization method: www.randomizer.org
Sample size: 60 subjects, 30 subjects in the study group, and 30 in the control group. The subjects have a referral to visit a specialist dentist/ periodontist
Main criteria for inclusion: Periodontal disease Stage III and Grade C with at least 6 sites with probing depth (PD) and clinical attachment loss (CAL) $\geq 5$ mm and bleeding on probing (BOP) $\geq 15$ teeth; aged $\geq 35$ ; smokers smoking $\geq 10$ cigarettes per day, at least 18 years old, presence of $\geq 20$ teeth, agreement to participate in the study and a written consent form signed.
Main criteria for exclusion: Presence of any physical limitation or restriction that might restrict Lumoral use, need for prophylactic antimicrobial coverage; scaling and root planing performed during the previous 6 months; non-smoking status or smoking less than 10 cigarettes per day; antimicrobial therapy in the previous 6 months; immune modifying conditions/ diseases (e.g., diabetes mellitus, rheumatoid arthritis, and osteoporosis); long-term use of medication that could interfere with periodontal response (e.g., bisphosphonates); pregnancy or lactation.

Comparative: None
Estimated duration of the data gathering in the clinical investigation: 6 months
Assessments:
Primary outcome: Difference in the number of reduced deep pockets (i.e. PD≤ 4mm, no BOP) between the test and the control group.
Secondary outcome: PD, CAL, BOP, Turetsky Modified Quigley-Hein Plaque Index (TMQHPI), levels of MMP-8, and Oral Health Quality of Life (OHQL). Need for optional SRP
Statistical methods: Wilcoxon test, Mann-Whitney U-test, Fisher's test, Pearson's correlation test

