## Study flowchart/ Schedule of visits and study procedures

Visit #/code	1	2	3	4	5	X
Reason for visit	Screening/ Baseline/	Start of the intervention	2-week follow- up/ SRP in 2 sessions in 2 weeks	10 -week follow-up	3 month follow- up	Termination
Inclusion/ exclusion criteria	x					
Informed consent	x					
Subject ID	x					
Subject demography	x					
Medications (changes*)	x				x*	
Oral and general disease history (changes*)	x				x*	
Assessments						
aMMMP-8 sampling (oral rinse)		x	x	x	x	
Potential Microbial sampling (periodontal pocket)		x		x	x	
Full mouth X-rays	x					
BOP%		x		x	x	
TMQHPI %		x	x	x	x	
PPD		x		x	x	
CAL		x		x	x	
Oral hygiene instructions		x	x	x	x	
Lumoral instructions (only study group)		x	x	x	x	
Lumoral diary for use (only study group)		x	x	x	x	
Reason for termination						x
AE/ADE/SAE/ SADE/DD			x	x	x	x

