### Power Calculation

Previous results showed statistically significant changes in plaque development in 15 patients in a randomized, split-mouth study (Nikinmaa et al. 2021a). In this clinical study plan, more effective antibacterial therapy shall be used. According to our published laboratory analysis, the dual-light antibacterial treatment would be at least a 3-log scale more potent than the treatment used in the split-mouth protocol (Nikinmaa 2021). In another pilot study in peri-implant patients using this more effective treatment, a significant change in plaque was already observed in the data of seven patients during four weeks of Lumoral treatment (Lähteenmäki et al., 2022).

Based on this limited but promising available data, a power calculation (SAS 9.4, Cary, NC, USA) was performed and levels for 5% alpha error and 20% TYPE II error (80% power) were determined. It was

concluded that the sample size of 25 patients in each study arm was sufficient to allow statistical calculations. 30 + 30 patients were assigned to cover possible dropouts.

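### The primary outcome is a raw count of closed pockets, capped by a varying baseline count, and no listed test compares the arms with allowance for that count

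*Combined protocol and SAP*

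**What the plan says.** The synopsis (Assessments) gives the primary outcome as "Difference in the number of reduced deep pockets (i.e. PD≤ 4mm, no BOP) between the test and the control group". This is a number per patient, with no denominator, percentage or baseline term. The statistical methods are one list, "Wilcoxon test, Mann-Whitney U-test, Fisher's test, Pearson's correlation test", with no test assigned to any outcome.

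Eligibility sets minimum values only: "at least 6 sites with probing depth (PD) and clinical attachment loss (CAL) $\geq 5$ mm" and "presence of $\geq 20$ teeth". Neither has an upper limit. The Methodology entry ("Randomized study; randomization method") names an online tool and mentions no stratification by extent of disease. The objective is set in "smoking periodontitis patients at 3 months".

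The study flowchart schedules probing depth and bleeding on probing at Visit 2 ("Start of the intervention") and again at Visit 5, the 3-month visit. The Power Calculation concludes that a "sample size of 25 patients in each study arm was sufficient to allow statistical calculations", raised to 30 per arm for dropout. It gives no effect size, SD or endpoint.

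**The concern.** A patient who starts with 10 deep pockets can close at most 10; one who starts with 60 can close 60. Part of the variation in the outcome therefore reflects how much disease patients brought to the trial, not how well they responded. A comparison that ignores the starting count leaves that variation in the error term.

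The listed tests do not remove it. A Mann-Whitney test on the count compares the arms without baseline. A paired Wilcoxon test uses baseline, but only within an arm. Pearson's correlation does not compare arms. Fisher's test on pooled pockets would use the denominators, but it would treat pockets in the same mouth as independent.

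Two things are at stake: precision, and the reading of the result if the arms happen to differ at baseline. Randomisation protects the long-run error rate, but not one trial of 25 to 30 patients per arm against a visible imbalance. An adjustment chosen after seeing such an imbalance would look data-driven.

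**Working it through.** **The plan's own figure.** With no effect size or SD, 25 per arm cannot be reproduced, only inverted. At two-sided 5% and 80% power it corresponds to a standardised difference of 0.81 (t-test). The step from 25 to 30 matches a dropout of one in six: 25 / (1 - 1/6) = 30. Nothing here tests whether 80% is reached.

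**Gain by formula.** If baseline and closed counts correlate r within arms, ANCOVA multiplies the error variance by 1 - r². The standardised effect becomes 0.809 / √(1 - r²). If the unadjusted difference in means has 80% power at 25 per arm:

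- r = 0.3: 0.809 / √0.91 = 0.848, power 84%
- r = 0.5: 0.809 / √0.75 = 0.934, power 90%
- r = 0.7: 0.809 / √0.51 = 1.133, power 98%

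**Gain by simulation.** From the documents: the floor of 6 sites, two equal arms, 25 or 30 per arm, 5% alpha (two-sided assumed). All else is assumed:

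- Baseline count is 6 plus a gamma variable, rounded.
- Closure is beta-binomial with a within-patient ICC, 45% in control v 60% in treated patients at the mean baseline count.
- Slopes are changes in closure log-odds per SD of baseline (control/treated).

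Five cases follow, all with mean baseline count 40. ANCOVA is the closed count on arm and baseline count with HC3 standard errors; Quade is its rank form.

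| SD, ICC, slopes | Mann-Whitney, 25 (30) per arm | ANCOVA, 25 (30) | Quade, 25 |
|---|---|---|---|
| 20, 0.10, 0/0 | 39% (45%) | 75% (83%) | 77% |
| 8, 0.20, 0/0 | 52% (59%) | 56% (65%) | 57% |
| 20, 0.10, -0.6/-0.6 | 62% (70%) | 64% (74%) | 69% |
| 20, 0.10, -0.9/-0.3 (effect grows with extent) | 73% (81%) | 82% (90%) | 80% |
| 20, 0.10, -0.3/-0.9 (effect shrinks with extent) | 37% (43%) | 33% (37%) | 44% |

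At 25 per arm the 95% CI half-width is 4.5 pockets adjusted v 7.3 unadjusted in the first case, but 4.6 v 4.7 in the third.

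The full grid had 360 scenarios: baseline mean/SD 20/5, 20/10, 40/8, 40/20, 60/12 and 60/30; ICC 0.05, 0.10 and 0.20; ten slope pairs; 25 and 30 per arm. Change in power against the raw-count Mann-Whitney, in percentage points:

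- ANCOVA: -8 to +62, median +4. It lost more than 1 point in 71 scenarios, and more than 3 only where the effect shrinks with extent.
- Quade: -1 to +64. It never lost more than 1 point.

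In ANCOVA's worst scenario (20/10, ICC 0.20, slopes -0.3/-0.9, 30 per arm) the powers were 25% for the unadjusted t-test, 26% for ANCOVA, 33% for Mann-Whitney and 36% for Quade. There the loss comes from leaving ranks rather than from adjusting.

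A separate simulation with other assumptions (closure 50% v 65%, mean 30 or 50, coefficient of variation 0.2 to 0.7, ICC 0.05 or 0.15, closure unrelated to extent, 25 per arm) gave 21% to 79% power for the raw count, 57% to 98% for ANCOVA and 61% to 96% for Quade.

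**Validity.** With no treatment effect (144 scenarios), Mann-Whitney rejected 3.8% to 5.7%, ANCOVA 3.3% to 5.1% and Quade 3.9% to 6.0%.

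**Chance imbalance.** The difference in mean baseline count has standard error SD × √(2/n). The probability that it reaches 0.5 SD is 2[1 - Φ(0.5 / √(2/n))]: 7.7% at n = 25 (z = 1.77) and 5.3% at n = 30 (z = 1.94). With SD 20 and 50% closure unrelated to extent, such an imbalance alone shifts the expected closed count by 0.5 × 20 × 0.5 = 5 pockets. The assumed treatment effect is (0.60 - 0.45) × 40 = 6 pockets. Rejection of a true null by the raw-count Mann-Whitney in those trials, at 25 and 30 per arm:

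- SD 20, ICC 0.10, slope 0: 28% and 32%
- the same, slope -0.3: 17% and 21%
- the same, slope -0.6: 7% and 8%
- SD 8, ICC 0.20, slope 0: 10% and 10%

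ANCOVA rejected 3% to 5% in all of these.

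**The case against.** An unadjusted randomised comparison is legitimate, and nothing here is invalid. The documents cannot say which scenario applies. The first case pairs a wide baseline spread with closure unrelated to extent; if closure falls with extent at the same spread, the ANCOVA gain is 2 points. All of this stands, and it is why no shortfall from 80% is claimed.

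The imbalance result is not a harm on top of the 5%. In the first case at 25 per arm, 28% of about 8% of trials contributes about 2.2 points, so the other 92% reject at about 3%. That is correct: the overall rate is unchanged. But a reader has one trial, and its baseline table will show which kind it was.

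A listed test could allow for the count if Mann-Whitney were applied to each patient's percentage closed. In a rerun of 2,000 replicates that gave 81% v 74% for ANCOVA in the first case, but 48% v 83% where the effect grows with extent. The stated outcome is a number, however, and the plan mentions no percentage.

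The strongest point concerns the remedy. On power alone Quade is safer than count ANCOVA and stays closer to the plan's rank tests. Nor do all ANCOVA losses come from leaving ranks: against the unadjusted t-test the change ranged from -5 to +68 points. What favours ANCOVA is that it estimates a difference in pockets with a confidence interval, which Quade does not. Either choice answers the concern.

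**Conclusion.** The concern holds as a matter of efficiency and robustness, not of bias or type I error. The outcome is capped by a baseline count that eligibility leaves free to vary, no stratification is stated, and the plan names no between-arm analysis that uses the count, although it is already collected.

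The size is uncertain. Under the assumed inputs the gain runs from negligible to very large (median 4 points for ANCOVA). The possible loss is at most about 8 points for ANCOVA and 1 for Quade. The benefit is large when baseline counts vary widely and predict the number closed; it is small when patients are similar at entry or when closure falls steeply with extent. The comparator throughout is a raw-count Mann-Whitney, itself an assumption because the plan assigns no test. The change should be made because it costs almost nothing.

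**What to change.** Keep the count as the endpoint and prespecify one patient-level primary analysis at 3 months (Visit 5):

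- **Outcome:** the number of each patient's baseline deep pockets that meet the plan's closure definition at Visit 5. The plan does not define a deep pocket. A probing depth of at least 5 mm at Visit 2, charted before the intervention starts, would follow the inclusion threshold.
- **Primary analysis:** ANCOVA of that count on arm and the Visit 2 deep-pocket count, with HC3 standard errors, reporting the adjusted difference in pockets with its 95% CI.
- **Sensitivity analyses:** Quade's rank ANCOVA, the unadjusted Mann-Whitney test, and the proportion closed per patient regressed on arm and log baseline count.

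Under the assumptions above, ANCOVA can cost up to about 3 points of power where baseline barely predicts the outcome and up to 8 where the effect shrinks with extent. If the team prefers rank tests, Quade can be primary, with the ANCOVA estimate and interval reported beside it.

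The cost is two or three sentences in the statistical methods, dated before the arms are compared. If they have already been compared, label the adjusted analysis post hoc.

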## Study flowchart/ Schedule of visits and study procedures

Visit #/code	1	2	3	4	5	X
Reason for visit	Screening/ Baseline/	Start of the intervention	2-week follow- up/ SRP in 2 sessions in 2 weeks	10 -week follow-up	3 month follow- up	Termination
Inclusion/ exclusion criteria	x					
Informed consent	x					
Subject ID	x					
Subject demography	x					
Medications (changes*)	x				x*	
Oral and general disease history (changes*)	x				x*	
Assessments						
aMMMP-8 sampling (oral rinse)		x	x	x	x	
Potential Microbial sampling (periodontal pocket)		x		x	x	
Full mouth X-rays	x					
BOP%		x		x	x	
TMQHPI %		x	x	x	x	
PPD		x		x	x	
CAL		x		x	x	
Oral hygiene instructions		x	x	x	x	
Lumoral instructions (only study group)		x	x	x	x	
Lumoral diary for use (only study group)		x	x	x	x	
Reason for termination						x
AE/ADE/SAE/ SADE/DD			x	x	x	x

### Power Calculation

Previous results showed statistically significant changes in plaque development in 15 patients in a randomized, split-mouth study (Nikinmaa et al. 2021a). In this clinical study plan, more effective antibacterial therapy shall be used. According to our published laboratory analysis, the dual-light antibacterial treatment would be at least a 3-log scale more potent than the treatment used in the split-mouth protocol (Nikinmaa 2021). In another pilot study in peri-implant patients using this more effective treatment, a significant change in plaque was already observed in the data of seven patients during four weeks of Lumoral treatment (Lähteenmäki et al., 2022).

Based on this limited but promising available data, a power calculation (SAS 9.4, Cary, NC, USA) was performed and levels for 5% alpha error and 20% TYPE II error (80% power) were determined. It was

concluded that the sample size of 25 patients in each study arm was sufficient to allow statistical calculations. 30 + 30 patients were assigned to cover possible dropouts.

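### The primary count of closed deep pockets has no assigned test and no adjustment for the number at entry, and the stated 80% power is not shown to apply to it

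*Combined protocol and SAP*

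**What the plan says.** **Outcome and tests (Overall synopsis, Assessments and Statistical methods).** The primary outcome is the difference between arms in how many deep pockets are brought to a probing depth of 4 mm or less with no bleeding. Wilcoxon, Mann-Whitney, Fisher and Pearson are listed for all outcomes together. No test is tied to the primary one.

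**Design (Overall synopsis).** The sample is "60 subjects, 30 subjects in the study group, and 30 in the control group", and the test arm is "compared to non-surgical periodontitis treatment alone". Entry requires disease "with at least 6 sites with probing depth (PD) and clinical attachment loss (CAL", with 5 mm as the limit. No maximum is set. Randomisation uses a web tool, and no stratification is mentioned.

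**Power (Power Calculation).** Two clinical sources are given: "Previous results showed statistically significant changes in plaque development in 15 patients in a randomized, split-mouth study", and a pilot in peri-implant patients in which "a significant change in plaque was already observed in the data of seven patients during four weeks of Lumoral treatment". A laboratory result on potency is added. The text continues: "Based on this limited but promising available data, a power calculation" was run, "levels for 5% alpha error and 20% TYPE II error (80% power) were determined", and it was "concluded that the sample size of 25 patients in each study arm was sufficient to allow statistical calculations". Thirty per arm allows for dropouts.

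**Measurements (Study flowchart).** Pocket depth, attachment level and bleeding are recorded at the start of the intervention, at 10 weeks and at 3 months.

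**The concern.** A patient who enters with many deep pockets can close many; one who enters with six can close at most six. In a raw count, that difference in opportunity is noise on top of any treatment effect. None of the listed methods removes it from an arm comparison, although the number at entry is already measured. The trial could then miss a benefit that the same patients would show under an adjusted analysis. A chance imbalance in baseline number would also stay uncorrected in the one trial that is run.

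The power statement gives no reassurance on this. A split-mouth comparison uses each patient as their own control, so it does not show between-patient spread. Plaque results do not give a difference in pocket closure.

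**Working it through.** **1. The plan's figure.** The 25 per arm cannot be reproduced, because no difference, SD, test or sidedness is given. It can only be solved backwards. With n = 2(1.960 + 0.842)²/d² per arm (two-sided 5%, 80% power), n = 25 gives d = √(15.70/25) = 0.79 SD. The noncentral t gives 0.81, and Mann-Whitney with efficiency 0.955 gives 0.81/√0.955 = 0.83. At 30 per arm the last two are 0.74 and 0.75. One-sided, 25 per arm gives 0.71 to 0.73. The documents link none of these values to pocket closure. The step from 25 to 30 allows 5/30 = 16.7% dropout.

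**2. What baseline spread does to the count.** The following inputs are assumptions; the documents give none. Central case: mean M = 30 deep sites, CV 0.5 (SD 15), within-patient correlation of closure ρ = 0.1, closure p = 50% against 65%.

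Variance of the closed count = p(1−p)[M(1−ρ) + ρE(N²)] + p²·SD², with E(N²) = 30² + 15² = 1125, so the bracket is 27 + 112.5 = 139.5.

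- Control: 0.25 × 139.5 + 0.25 × 225 = 34.9 + 56.3 = 91.1
- Test: 0.2275 × 139.5 + 0.4225 × 225 = 31.7 + 95.1 = 126.8
- Raw: SD = √((91.1 + 126.8)/2) = 10.4; difference 30 × 0.15 = 4.5; ratio 0.43 SD
- Baseline part removed: SD = √((34.9 + 31.7)/2) = 5.8; ratio 4.5/5.8 = 0.78 SD

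At CV 0.1 (SD 3, E(N²) = 909) the same formula gives about 0.81 SD raw and 0.85 SD adjusted, so the gain nearly vanishes.

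**3. Simulated power.** Baseline number is 6 plus a negative binomial and closure is beta-binomial; 25 per arm unless stated, two-sided 5%, 50% against 65% unless stated. There were 1,500 runs per scenario in the main grid.

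| Setting (mean, CV, ρ) | Mann-Whitney, raw count | Mann-Whitney, percentage closed | Covariance analysis, baseline number |
|---|---|---|---|
| Range over 18 scenarios: 20 or 40; 0.3-0.7; 0.05-0.2 | 20-64% | 53-96% | 45-96% |
| Smallest gain: 20, 0.3, 0.2 | 43% | 57% | 57% |
| Largest gain: 40, 0.7, 0.05 | 24% | 94% | 92% |
| Central: 30, 0.5, 0.1 | 35% | 80% | 76% |
| Central, 30 per arm | 39% | 86% | 84% |
| Central, 30% against 45% | 53% | 80% | 76% |
| Central, 70% against 80% | 14% | 58% | 51% |
| Central, closure falls moderately with baseline number | 42% | 73% | 73% |
| Central, closure falls strongly | 53% | 62% | 74% |
| Outside grid: 20, 0.1, 0.1 | 73% | 78% | 80% |
| Outside grid: 30, 0.1, 0.1 | 75% | 81% | 80% |
| Outside grid: 30, 0.2, 0.2 | 51% | 60% | 60% |
| Outside grid: 20, 0.3, 0.4 | 28% | 35% | 30% |

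Repeat runs of the central case gave 32-36% raw, about 78% on percentage closed and 74-77% with the covariate. The last four rows used 1,000 runs each, with a simulation error up to √(0.25/1000) = 1.6 points per figure. Their covariate gains are 2 to 9 points; further runs in that region put the gain at about 4 to 12. These limits are approximate.

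For a larger effect, 50% against 80%, raw-count power is about 98% at CV 0.3 and 80-82% at CV 0.5 (mean 30, ρ = 0.1).

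**4. Validity.** With no treatment effect (4,000 runs), the three analyses reject in 5.5%, 5.4% and 5.6% of trials.

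**5. Chance imbalance.** The standard error of the relative difference in mean baseline number is CV × √(2/25). At CV 0.5 this is 0.141, so a gap of 20% or more (0.20/0.141 = 1.41 standard errors) arises in 15.7% of trials. At CV 0.3 and 0.7 it is 1.8% and 31%.

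**The case against.** **No test is prescribed.** A reader might infer that the plan commits to an unadjusted test. It does not: four tests are listed for several outcomes. Fisher's test could even be applied to pockets closed against not closed, which uses the number at entry at arm level but ignores clustering within patients. This stands. Mann-Whitney on the count is only the natural reading for two arms, and the supportable statement is that no listed method adjusts for baseline.

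**The size rests on assumed inputs.** The documents give no mean or spread of baseline number, and the population is fairly narrow (Stage III, Grade C, heavy smokers, at least 20 teeth). The 15-point closure difference is also assumed. This stands: with little spread, high within-patient correlation or a large effect, the raw count loses little. But a floor without a ceiling gives no assurance that spread is small.

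**Imbalance does not create false positives.** One might infer that unequal baseline numbers could produce a spurious effect more often than the nominal rate. Under randomisation, the 5% error rate already covers this. The cost is precision.

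**The power sources are mixed.** Only the 15-patient study is described as split-mouth. The pilot is described as a change over four weeks, its design is not stated, and the laboratory figure is not patient data. The basis should not be called wholly within-patient. Even so, none of the three, as described, supplies a closure difference or a between-patient SD.

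**Conclusion.** The point holds as one of efficiency and of unsupported power. Within the assumed grid, using baseline number raises power from about 20-64% to 45-96%, at least 14 points in every scenario. Outside it (CV of 0.2 or less, or correlation of 0.4), the gain is about 4 to 12 points. For closure of 50% against 80%, the raw count already reaches about 80% or more when CV is 0.5 or below. The true size is unknown because the documents do not give the inputs.

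A reader might conclude that the trial is too small. The documents do not support that: they show only that the 80% has not been tied to pocket closure. Twenty-five per arm could be enough if the effect is large, if baseline spread is small or if the analysis adjusts for it.

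**What to change.** Keep N and the endpoint.

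**(a) Name one primary analysis before outcome data are seen.** For example: the per-patient number of baseline deep pockets closed at 3 months is compared between arms by analysis of covariance with baseline number of deep pockets as covariate, two-sided 5%, reported with a 95% confidence interval. State explicitly that a deep pocket is a site meeting the entry definition. Use Mann-Whitney on the per-patient percentage closed as the sensitivity analysis.

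**(b) In the Power Calculation section, state which outcome and inputs the SAS calculation used.** If the outcome was plaque, do not present the 80% as power for pocket closure. Give instead, labelled illustrative, the difference detectable at the fixed N: about 0.81-0.83 SD at 25 per arm and 0.74-0.75 SD at 30 per arm, two-sided 5%.

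**Cost.** No patients, visits or measurements are added; the baseline readings are already scheduled. The covariance model assumes a roughly linear relation with baseline number and an additive effect, and percentages are noisy in patients with few deep sites. A clustered binomial model would also be defensible. What matters is to choose one in advance.
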